## 6.11. Imaging Acquisition, Archival, and Interpretation

### 6.11.1. Overview

Two MR examinations will be performed: a pre-hepatectomy MR examination on subjects (Section 6.11.2) and an *ex-vivo* MR examination on the resected specimen (Section 6.11.4). Both MR examinations will be performed on the same 3T research scanner. The only identifying information entered into the scanner will be the subject's study ID and date of birth. The study radiologist will analyze the pre-hepatectomy MRI only. The PI and other study investigators will use the combined information from the pre-hepatectomy MRI, *ex-vivo* MRI, and pathology specimen to define the surgical margin on the pre-hepatectomy images and to generate a lesion reference standard table (Section 6.13).

### 6.11.2. Pre-hepatectomy MR imaging acquisition

#### 6.11.2.1 Subject safety.

The PI or a study investigator will monitor the subject for adverse events from subject arrival to departure from the MR facility. Adverse events will be recorded (Section 8.0).

#### 6.11.2.2 Subject preparation.

Subjects will be instructed to fast for a minimum of two hours prior to MRI. A certified technologist or other qualified medical professional will insert an intravenous catheter. The site and gauge of the catheter access will be noted. When intravenous access cannot be obtained, the use of centrally placed intravenous access (port) is acceptable if the subject has such access placed for clinical reasons and if the port is graded for use with a power injector. Subjects will be positioned supine, and a dielectric pad and an 8-element phase array coil will be centered over the abdomen at the level of the liver.

#### 6.11.2.3 Gd-based contrast media.

Gadobenate dimeglumine (MultiHance, Bracco) at a dose of 0.1 mmol/kg (maximum dose of 10 mmol for subjects  $\geq$  100 kg) will be injected at 2 ml/sec using a power injector followed by a 20 ml saline flush at the same rate.

#### 6.11.2.4 Examination quality.

The PI will monitor the MRI exams for image quality. Artifacts sequences will be repeated. The research coordinator will track the successful acquisition of each sequence on a data entry sheet and record what sequences were repeated.

#### 6.11.2.4. MR protocol.

The following protocol will be programmed into the research scanner (“CRC Protocol”). This protocol will take about 90 minutes: 30 minute from the beginning of the preparatory sequences through the completion of Image Set 8, a 55-minute break between Image Set 8 and Image Set 9 during which the subject can be taken out of the scanner depending on subject preference, and about one minute to acquire Image Set 9.

- Preparatory sequences (will not be analyzed)
  - Localizer
  - Parallel imaging calibration scan
  - Coronal T2w SSFSE: TR 1500, TE 90, matrix 320x192, slice thickness 8 mm, gap 0 mm, bandwidth 100 kHz, parallel imaging off. Options: SCIC, extended dynamic range.
- **Image Set 1.**
  - Axial T2w SSFSE: TR 1500, TE 90, matrix 320x224, slice thickness 5 mm, gap 0 mm, bandwidth 83 kHz, parallel imaging on (acceleration factor = 2). Options: SCIC, extended dynamic range. FOV 30 to 50 cm depending on body habitus. Phase FOV 100%.
- **Image Set 2.**
  - Axial T2w FRFSE: **Parameters pending**. Same FOV as Image Set 1.
- **Image Set 3.**
  - Axial T1w SPGR: TR 200-300 depending on breathhold capacity and liver size, TE 2.3, flip angle 70, matrix 320x224, slice thickness 5 mm, gap 0 mm, bandwidth 62.5 kHz, parallel imaging on (acceleration factor = 2). Options: SCIC, extended dynamic range. Same FOV as Image Set 1.
- **Image Set 4.**
  - Axial six-echo SPGR: TR 200-300 depending on breathhold capacity and liver size, TE 2.3, 4.6, 6.9, 9.2, 11.5, 13.8, matrix 320x224, slice thickness 5 mm, gap 0 mm, bandwidth **141 (check)** kHz, parallel imaging on (acceleration factor = 2). Options: extended dynamic range. We have previously confirmed that the exact TR does not affect the estimated T2\* value. Same FOV as Image Set 1.
  - Repeat.
- **Image Set 5.**
  - Axial six-b-value DW EPI: TR 2500-3500 depending on breathhold capacity and liver size, TE 50 msec, b-values of 0, 10, 50, 250, 500, 750 sec/mm^2, matrix 128x160, slice thickness 10 mm, gap 0 mm, bandwidth 62.5 kHz, parallel imaging on (acceleration factor = 2). Options: extended dynamic range, zoom gradient, one prep scan, b-value order reversed. We have previously confirmed that the exact TR does not affect the estimated ADC value. Same FOV as Image Set 1.
  - Repeat.
- **Image Set 6.**
  - Axial MR elastography with wave frequency of 60 Hz. **Parameters pending**. Same FOV as Image Set 1?
  - Repeat.
- **Image Set 7.**
  - Dynamic 3D T1w LAVA: TR min, TE min, matrix 320x224, FA 15, slice thickness 4 mm, bandwidth 100 kHz, parallel imaging on (acceleration factor = 2). Options: SCIC, extended dynamic range, zip 2, zoom gradient (if FOV ≤ 35 mm). Obtain before and 20,

80, and 180 seconds after injection of 0.1 mmol/kg gadobenate dimeglumine (MultiHance, Bracco) at 2 ml/sec followed by 20 ml saline flush. Same FOV as Image Set 1.

- **Image Set 8.**
  - Late venous phase LAVA: 5 minutes. Same FOV and other parameters as Image Set 7.
- **Image Set 9.**
  - Hepatocellular phase LAVA: 60 minutes. Same FOV and other parameters as Image Set 7.

### **6.11.3. Pre-hepatectomy MR imaging interpretation**

#### 6.11.3.1. Overview.

The study radiologist will have expertise in MRI of the liver. The radiologist will be trained on a test set to become familiar with the imaging criteria. After the training, the radiologist will review and interpret the pre-hepatectomy research exams. The radiologist will know the subject's study ID and date of birth, and will be aware that the subject has a pre-operative diagnosis of CRC metastasis to the liver. The coordinator will explain to the radiologist the segment(s) that were resected at surgery. The radiologist will be blinded to all other information. MR images (test set and research exams) will be reviewed on high-resolution >4 megapixel gray-scale monitors using the hospital PACS system.

#### 6.11.3.2. Training.

The radiologist will be trained on a test set of 3T MR images obtained on non-study subjects. The test set will include examples of CRC metastases and benign lesions (hemangiomas, cysts, focal nodular hyperplasias, and transient hepatic intensity differences). During the training phase, the imaging criteria outlined below will be defined.

#### 6.11.3.3. Interpretation.

The radiologist will review the nine image sets in a different random order in one reading session for each subject. (Reviewing each image set in a different session is not feasible). The random order of review will reduce bias in the performance of one image set relative to another. During the review of each image set, the radiologist will flag each detected nodule, number each new nodule consecutively, and characterize the corresponding nodule feature(s) as outlined in the Table below. If the radiologist identifies nodules on one image set that were missed on a prior image set, the radiologist will re-review the prior image set and retrospectively characterize the corresponding nodule features. The initial interpretations will be used for specific aim 1 and the final interpretations for specific aim 2. After the nine image sets are reviewed, the radiologist will review all the images in conjunction and score ten global lesion features. The radiologist also will score two per-patient features (anterioposterior skin-to-skin diameter of the abdomen [contiguous] and presence of ascites [four-point ordinal: none, mild, moderate, severe]), as these may conceivably affect image quality.

The research coordinator will enter the radiologist's per-lesion and per-patient interpretations into a data entry sheet. Representative screen capture images showing the

location and identifier of each lesion detected by the study radiologist will be exported in JPEG format. Under the radiologist's supervision, the research coordinator will place regions of interest on image sets 4-6 and record the T2\*, ADC, shear modulus values for each nodule and for each of the repeated acquisitions. Both repeated measurements will be used in the analysis of intraclass correlation coefficient. Only the first of the repeated measurements will be used in the sensitivity, specificity, and ROC analyses.

Image Set	Feature	Categories
1 T2w SSFSE	Signal intensity	Homogeneous 
 
• Markedly hypo-intense
 
• Hypo-intense
 
• Iso-intense
 
• Hyper-intense
 
• Markedly hyper-intense
 
 Heterogeneous
2 T2w FRFSE	Signal intensity	Homogeneous 
 
• Markedly hypo-intense
 
• Hypo-intense
 
• Iso-intense
 
• Hyper-intense
 
• Markedly hyper-intense
 
 Heterogeneous
3 T1w SPGR	Signal intensity	Homogeneous 
 
• Markedly hypo-intense
 
• Hypo-intense
 
• Iso-intense
 
• Hyper-intense
 
• Markedly hyper-intense
 
 Heterogeneous
4 Six-echo SPGR	T2*	Continuous
5 DWI	ADC	Continuous
6 MRE	Shear modulus	Continuous
7 Dynamic 3D T1w	Kinetics	Homogeneous 
 
• With retention
 
• With fade
 
• With washout
 
 Ring 
 
• With retention
 
• With fade/washout
 
 Heterogeneous Puddles with retention
8 Late venous phase	Signal intensity	
 
• Hypo-intense
 
• Iso-intense
 
• Hyper-intense
 

9 Hepatocellular phase	Signal intensity	
 
• Hypo-intense
 
• Iso-intense
 
• Hyper-intense
 

Global	Long axis diameter	Continuous
	Short axis diameter	Continuous
	Shape	
 
• Round/oval
 
• Lobulated
 
• Irregular
 
• Geographic/polygonal
 
• Wedge
 
• Linear
 

	Margins	
 
• Sharp
 
• Mixed
 
• Indistinct
 

	Central heterogeneity	
 
• Yes, consistent with scar
 
• Yes, consistent with necrosis
 
• Yes, uncertain if necrosis or scar
 
• No
 

	Pseudo-capsule	
 
• Yes
 
• No
 

	Transient hepatic intensity difference	
 
• Yes – wedge shaped
 
• Yes – peri-lesional halo
 
• No
 

	Internal arteries	
 
• Yes
 
• No
 

	Draining veins	
 
• Yes
 
• No
 

	Edema around lesion	
 
• Yes
 
• No
 

	Distance from nearest surface	Continuous
	Overall confidence for cancer	
 
• 0 definitely not cancer
 
• 1 probably not cancer
 
• 2 possibly not cancer
 
• 3 indeterminate
 
• 4 possibly cancer
 
• 5 probably cancer
 
• 6 definitely cancer
 

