## **9.0 STATISTICAL CONSIDERATIONS**

### **9.1 Study Design and Endpoints**

#### **9.1.1. General study design.**

This is a prospective cohort pilot study assessing 3T MRI for diagnosis of CRC metastases to the liver in pre-hepatectomy patients. Consecutive eligible subjects with CRC metastases to the liver will undergo a research MRI of the liver within one week prior to curative hepatectomy done for clinical care. One radiologist will review the MR images and, for each focal lesion (benign or malignant) identified at imaging on each subject, assess 21 imaging features such as size, shape, margination, heterogeneity, kinetic enhancement pattern, and overall confidence for malignancy. Features will include binary, categorical, ordinal, and continuous variables. Sixteen features will be standard and five (T2\*, ADC, shear modulus, late venous phase signal intensity, and hepatocellular phase signal intensity) will be experimental. The MR sequences used to obtain the three quantitative experimental lesion features (T2\*, ADC, shear modulus) will be acquired twice for each subject. The radiologist also will assess two-per patient imaging features (abdominal AP diameter at the level of the portal vein bifurcation and the presence of ascites). Three demographic features (subject age, gender, ethnicity) will be available for the multivariate analyses; of the three, age will potentially be known to the radiologist as the scans will include the subject's date of birth.

For each subject, the lesions included in the analysis will be those identified at pre-hepatectomy imaging, *ex-vivo* imaging, pathology, or any combination of the three. The reference standard for each lesion will be the dichotomized histological diagnosis (malignancy versus other). Subjects are expected to have between one and ten CRC metastases in the hepatectomy specimen (average of three) and zero to five benign lesions (average of one). Subjects are not expected to have any malignancies other than CRC metastases.

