**9.1.2.2. Secondary aims.**

9.1.2.2.1. Secondary aim 1.

9.1.2.2.1.2. Aim.

Estimate and compare the per-lesion area under the ROC curve of a multivariate model that uses experimental as well as standard MRI features versus that of a model that uses only standard MRI features for the diagnosis of CRC metastases. Both models may use per-patient features such as age, gender, ethnicity, ascites, and anteroposterior diameter.

9.1.2.2.1.2. Analysis plan for secondary aim 1.

Using all available per-lesion MRI features (standard and experimental), per-subject MRI features (anteroposterior diameter and ascites), and per-subject clinical features (age, gender, ethnicity), multivariate models will be constructed to assess the discriminatory ability of each MRI feature after adjusting for the other features.

Other multivariate models will be constructed after excluding experimental features from consideration.

The area under the ROC curves corresponding to these models will be compared. To account for clustering due to multiple lesions for some patients and multiple observations per lesion, generalized estimating equation techniques will be used. The model with the largest area under the ROC curve will be identified.

9.1.2.2.2. Secondary aim 2.

9.1.2.2.1. Aim: Estimate the intraclass correlation coefficient of repeated quantitative measurements (T2\*, ADC, and shear modulus) on each lesion.

9.1.2.2.1.2. Analysis plan for secondary aim 2. The intra-class correlation coefficient between repeated measures will be calculated.

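### The standard-only model in secondary aim 1 may include an overall-confidence rating scored with the experimental images in view, which would shrink the measured AUC gain

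*Protocol*

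**What the plan says.** Section 9.1.1 has the radiologist "assess 21 imaging features such as size, shape, margination, heterogeneity, kinetic enhancement pattern, and overall confidence for malignancy". It divides them as follows: "Sixteen features will be standard and five" experimental, the five being T2*, ADC, shear modulus, late venous signal intensity and hepatocellular signal intensity. Overall confidence is among the 21 and is not one of the five.

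Section 6.11.3.3 sets out the reading. "The radiologist will review the nine image sets in a different random order in one reading session for each subject". A nodule first noticed on a later set triggers a second look at the sets already read: "the radiologist will re-review the prior image set and retrospectively characterize the corresponding nodule features". Then: "After the nine image sets are reviewed, the radiologist will review all the images in conjunction and score ten global lesion features". The feature table in that section lists "Overall confidence for cancer", on a scale of 0 to 6, in its Global block. On which readings are used, the section says: "The initial interpretations will be used for specific aim 1 and the final interpretations for specific aim 2".

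The analysis plan for secondary aim 1 (under Section 9.2) first builds models from all available features, and then says: "Other multivariate models will be constructed after excluding experimental features from consideration". The AUCs of the two kinds of model are compared. Nothing asks for a confidence score based on the standard sets alone, and nothing removes overall confidence from either model.

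**The concern.** The comparison is meant to show what the experimental sequences add to a conventional reading. That requires a comparator free of experimental information. Overall confidence is the reader's own synthesis of everything on the screen, given once all nine image sets have been seen. As a direct rating of malignancy, it is likely to be a strong predictor wherever it is offered to a model.

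If it enters the standard-only model, part or all of the experimental contribution is credited to the comparator, and the AUC difference moves toward zero. Section 1.0 says the pilot will be used to plan a trial that assesses these models further, so an understated increment could carry into that planning. A statistical analysis plan could discard the rating. It could not recover an uncontaminated one, because the protocol collects the score once, with every image in view.

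**Working it through.** **Step 1: is overall confidence a standard feature?** The table in Section 6.11.3.3 has one feature for each of image sets 1 to 9 and 12 rows in the Global block.

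- Total: 9 + 12 = 21, which matches Section 9.1.1.
- Standard: 21 − 5 = 16, which also matches. These are 4 single-set features (sets 1, 2, 3 and 7) and 12 global ones.
- If only the ten global features mentioned in the text are counted: 9 + 10 = 19 in total and 19 − 5 = 14 standard. Neither matches.

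The protocol's 16 and 21 are reached only if all 12 global rows, overall confidence included, are standard.

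**Step 2: what has the reader seen when scoring it?** The five experimental features come from sets 4, 5, 6, 8 and 9. The global features are scored after all nine sets, with all images available together, so these five sets are in view.

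**Step 3: is it removed from the comparator?** No. Only the experimental features are excluded, and overall confidence remains a candidate.

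**Step 4: how large could the effect be?** The documents give no AUC for either model, so these inputs are assumptions: binormal scores; standard information S and experimental information E independent within class, each with AUC 0.75; and confidence = S + E + noise, with noise variance v in units of the within-class variance of S or E.

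- Separation of each source: d = √2 × z(0.75) = 1.414 × 0.6745 = 0.954, so d² = 0.910.
- Clean standard-only AUC: Φ(d/√2) = 0.75.
- AUC with both sources: Φ(√(2d²)/√2) = Φ(0.954) = 0.83. The true gain is 0.08.
- Standard-only AUC once confidence is in the model: Φ(√(d² + d²/(1+v))/√2).

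| v | Standard-only AUC | Visible gain |
|---|---|---|
| 0 | 0.83 | 0.00 |
| 0.25 | 0.82 | 0.01 |
| 1 | 0.80 | 0.03 |
| 2 | 0.78 | 0.05 |

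A second parametrisation lets confidence carry a share w of the experimental signal: standard-only AUC = Φ(√(d_S² + w²d_E²)/√2). With a clean standard AUC of 0.80 and an experimental AUC of 0.75, the combined AUC is 0.860 and the true gain 0.060. At w = 0.5, 0.75 and 1 the visible gain is 0.042, 0.023 and 0. Over standard AUCs of 0.75 to 0.85 and experimental AUCs of 0.70 to 0.75, the true gain runs from 0.027 to 0.080; it shrinks to 0.020 to 0.055 at w = 0.5 and to zero at w = 1.

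**Step 5: would using the initial readings cure this?** No. Take one standard set and the five experimental sets in random order: the standard set comes first of the six with probability 1/6. An initial reading of it therefore follows at least one experimental set with probability 1 − 1/6 = 5/6, or 83%. The global scores come after all nine sets in any case.

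**The case against.** Five objections deserve an answer.

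**Candidate, not forced predictor.** The plan names a pool of features and does not say that overall confidence must be used. Selection rules may sit in a statistical analysis plan that is not shown. This stands: a reader might infer that the gain is masked as a matter of fact, but the text supports only that it can be attenuated.

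**The other global features.** Since 12 of the 16 standard features are scored with every image in view, a reader might infer that most of the comparator is contaminated. The documents do not support that. Diameters, distance from the surface, shape, margins and vessels describe size and morphology, and nothing shows that seeing a diffusion image makes a diameter carry ADC. Also, T2*, ADC and shear modulus are region-of-interest values recorded by the coordinator under the radiologist's supervision, and the protocol does not say the reader has them when scoring confidence. The reader does have the images, so the concern stands for confidence and is speculative for most of the rest.

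**The re-readings.** A reader might infer that the final readings carry experimental information into the single-set features. That is weak. Re-readings affect only nodules missed on an earlier set, the set that revealed them may itself be standard, and the value recorded is still the signal on the standard set. The link to this comparison is also inferred: specific aim 2 is not a label used in the aims. It most plausibly means the multivariate comparison, because the other secondary aim rests on repeated quantitative measurements.

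**Ten or twelve global features.** One could argue that confidence is one of two rows outside the ten. It is nevertheless listed as global and is an overall judgement, and no separate earlier scoring is described.

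**Overfitting works the other way.** About 90 malignant and 30 benign lesions are expected (30 subjects, averages of three and one). In a simulation of that size with 16 + 5 predictors, an in-sample linear discriminant and independent lesions, five pure-noise experimental features produced a mean apparent gain of 0.022. A real clean signal gave about 0.07, and about 0.04 with contaminated confidence at v = 1. The attenuation is real, but the gain finally reported could be pushed either way. This limits any prediction of the observed figure; it does not justify the contaminated comparator.

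**Conclusion.** The point holds for overall confidence. It is a standard feature by the protocol's own count, is scored with the experimental images in view, and remains available to the standard-only model. If that model uses it, the AUC gain in secondary aim 1 is biased toward zero, and fully hidden in the extreme case. In the illustration a true gain of 0.08 falls to between 0.00 and 0.05. That range rests on independence, binormal scores, AUC 0.75 for each source and noise variance from 0 to 2; none of these comes from the documents, and the actual size cannot be derived from them.

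The documents do not establish that the gain will be masked, that the size and morphology features are contaminated, or that the re-readings do material harm. The single-feature estimates of the primary aim and the intraclass correlation aim are not affected. For a secondary aim of a 30-subject pilot, this is a should-fix point.

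**What to change.** In the analysis plan for secondary aim 1, exclude overall confidence for cancer from the candidate features of both multivariate models, and analyse it only as a single feature in the primary aim. This needs no new scan, reading or subject. The cost is one probably strong predictor lost from both models.

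Three clarifications should go with it:

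- Use the same type of reading, initial or final, in both models. Initial readings in the standard-only model alone would make the two models differ in reading type as well as in features. Nodules missed at first would also have no standard values there, so the lesion sets could differ.
- State in Section 6.11.3.3 which aim specific aim 2 refers to.
- Reconcile the ten global features in the text of that section with the twelve in its table.

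A staged reading is optional: read sets 1, 2, 3 and 7 first, lock the global scores and confidence, then open the experimental sets and score again. It would give a clean standard-only confidence score at the price of one rescoring per lesion. It also gives up full randomisation of reading order across the nine sets, which Section 6.11.3.3 adopts to limit bias between image sets. Experimental sets would always follow standard ones, and that could affect the primary-aim estimates. It should therefore not be the default remedy.

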## **9.2 Specific Aims and Analysis Plans**

#### **9.1.3.1. Primary aim.**

9.1.3.1.1. Aim: For each MRI feature, estimate the per-lesion sensitivity and specificity (binary and dichotomized categorical features) or the area under the ROC curve (ordinal and continuous features) for the diagnosis of CRC metastases.

9.1.3.1.2. Analysis plan:

Frequency tables of the per-lesion MR features will be generated for non-continuous features. Descriptive statistics (e.g., mean, median, variance) will be used to summarize continuous features.

For each binary or dichotomized categorical feature, lesions will be classified as:

- True positive: lesion feature is positive and lesion histology is malignant
- False positive: lesion feature is positive and lesion histology is benign
- True negative: lesion feature is negative and lesion histology is benign
- False negative: lesion feature is negative and lesion histology is malignant

From this classification, the per-lesion sensitivity and specificity for the diagnosis of malignancy will be estimated. Corresponding 95% confidence intervals will be calculated using clustered data methods that can accommodate multiple lesions per patient and multiple observations per lesion.

For ordinal and continuous features, the ROC curve for the per-lesion diagnosis of malignancy will be generated and the area under the ROC curve calculated using empirical method. Corresponding 95% confidence intervals will be calculated using clustered data methods that can accommodate multiple lesions per patient and multiple observations per lesion. If the 95% confidence interval for the AUC contains the null hypothesis value of 0.5, then we will conclude that the corresponding feature does not have discriminatory ability.

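### Section 6.11.3.3 limits the ROC analyses to the first T2\*, ADC and shear-modulus acquisition, Section 9.2 plans them for several observations per lesion, and using both acquisitions would tighten the AUC intervals without changing what is estimated

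*Protocol*

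**What the plan says.** Section 9.1.1 states that the sequences behind the three quantitative experimental features "will be acquired twice for each subject". Section 6.11.3.3 then assigns the two sets of values. For reliability: "Both repeated measurements will be used in the analysis of intraclass correlation coefficient". For accuracy: "Only the first of the repeated measurements will be used in the sensitivity, specificity, and ROC analyses".

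Section 9.2 neither repeats nor cites that rule.

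- **Primary aim.** The confidence intervals for sensitivity, specificity and AUC are to come from "clustered data methods that can accommodate multiple lesions per patient and multiple observations per lesion".
- **Secondary aim 1.** For the comparison of model AUCs: "To account for clustering due to multiple lesions for some patients and multiple observations per lesion, generalized estimating equation techniques will be used".

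The primary plan also attaches a decision to each AUC interval: if it contains 0.5, the feature is declared not to discriminate.

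**The concern.** The statistical section describes a data set with several observations per lesion. The interpretation section permits one. An analyst working from Section 9.2 alone would not see the first-only rule and would have to choose between first value, both values as rows, or the average.

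The choice has consequences. It sets the number of rows and the variance calculation for three of the five experimental features. If the repeats are averaged, it also changes the AUC being estimated. In the multivariate models, two rows per lesion would duplicate every feature that is not repeated (21 − 3 = 18). Because the interval decides whether a feature is said to discriminate, the input should be fixed in one way before the data are seen.

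There is also an efficiency question. The second values are acquired and recorded for every nodule, and a clustered method is already planned. The point to check is how much precision first-only gives up.

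**Working it through.** **1. Is there another source of repeats?** Section 9.1.1 has one reader: "One radiologist will review the MR images". Section 6.11.3.3 has one reading session per subject and divides the readings by aim: "The initial interpretations will be used for specific aim 1 and the final interpretations for specific aim 2". Initial and final readings are therefore not pooled in one analysis. The duplicate acquisitions are the only evident source of several observations per lesion, and the first-only rule removes them from the ROC analyses.

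**2. The plan's own figures (Section 9.3).**
- Precision: 1.96 × √(0.25/30) = 0.179, which matches the stated 18%.
- Power for AUC 0.7 against 0.5: 30 subjects × 4 lesions, 75% malignant, gives 90 malignant and 30 benign lesions. The design effect is 1 + (4 − 1) × 0.5 = 2.5, leaving an effective 36 and 12.
- Hanley–McNeil: Q₁ = 0.7/1.3 = 0.5385 and Q₂ = 0.98/1.7 = 0.5765. Variance = [0.21 + 35 × 0.0485 + 11 × 0.0865]/432 = 0.0066, so SE = 0.081.
- The Wald test then gives 79.2% power one-sided and 69.1% two-sided. The stated 80% is reproduced one-sided; the protocol does not state sidedness.

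Neither figure counts a second acquisition, which fits the first-only rule.

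**3. What would the second acquisition add?** The protocol gives no repeat ICC, so a range is assumed. The simulation has 30 subjects, each with 3 malignant and 1 benign lesion. A measurement is a subject effect (variance 0.5 × ICC), plus a lesion effect (0.5 × ICC), plus error (1 − ICC), plus a malignant shift that gives a single-acquisition AUC of 0.70. The SE is the standard deviation of the empirical AUC across simulated studies.

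| Repeat ICC | SE, first only | SE, both as clustered rows | Reduction |
|---|---|---|---|
| 0.5 | 0.048 | 0.039 | 1 − 0.039/0.048 = 19% |
| 0.7 | 0.046 | 0.040 | 13% |
| 0.8 | 0.045 | 0.041 | 9% |
| 0.9 | 0.043 | 0.041 | 5% |
| 0.95 | 0.043 | 0.042 | about 3% before rounding |

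The mean AUC stays at 0.70 in both columns, and a clustered (Obuchowski) variance keeps coverage near 94–95%. These SEs are smaller than the 0.081 in step 2 because the shared subject effect partly cancels when malignant and benign lesions come from the same subject.

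**4. Sensitivity to the model.** With the subject variance fixed at 0.5 of the total, the SE goes from 0.0415 to 0.0326 at ICC 0.6 (21%), 0.0411 to 0.0374 at 0.8 (9%), 0.0418 to 0.0394 at 0.9 (6%) and 0.0424 to 0.0412 at 0.95 (3%). With lesion counts varying between subjects, at ICC 0.9, it goes from 0.0568 to 0.0544 (4%).

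**5. Rows or average?** Under a binormal model, averaging gives AUC = Φ(Φ⁻¹(0.70) × √(2/(1 + ICC))). That is 0.728 at ICC 0.5, 0.710 at 0.8 and 0.702 at 0.95. Averaging changes the estimand; separate rows do not.

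**6. Effect on the 0.5 rule.** At AUC 0.70 and ICC 0.5, the chance that the interval excludes 0.5 is Φ(0.2/0.048 − 1.96) = 98.6% with the first acquisition and Φ(0.2/0.039 − 1.96) = 99.9% with both. At a true AUC of 0.60 and ICC 0.8, simulation gives 0.55 with the first and 0.64 with both.

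**The case against.** In favour of the plan as written, Section 6.11.3.3 contains the only explicit selection rule, that rule covers all ROC analyses, and no sentence in Section 9.2 tells the analyst to enter two rows. First-only estimates the accuracy of one acquisition and gives every feature the same data structure. The repeats come from one examination, so their ICC may be high and the gain small: the 95% half-width changes by 1.96 × 0.002 = 0.004 at ICC 0.9 and 1.96 × 0.004 = 0.008 at ICC 0.8. Row layout is often left to a SAP, and this is a pilot aimed at estimation.

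Much of this stands. First-only is legitimate, and at high ICC little is lost. The primary-aim wording describes what the methods are able to handle, which is compatible with one observation per lesion, so it is not a contradiction in itself. The objection fails for secondary aim 1, which names repeats per lesion as clustering that is present. Nor is this a matter left open for a SAP, since the protocol addresses it in two places that do not agree. Keeping the single-acquisition estimand does not require dropping the second values either, as steps 3 and 5 show.

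A reader might infer that half the quantitative data are thrown away for nothing. The documents do not support that. The second acquisitions are the data for secondary aim 2. Two correlated values on a lesion also carry the information of 2/(1 + ICC) independent ones for that lesion's mean, which is 1.33 at ICC 0.5 and 1.03 at 0.95, not 2.

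**Conclusion.** The plan for secondary aim 1 does not fit the rule in Section 6.11.3.3 and the two should be reconciled; the primary-aim wording needs only a clarification. It would be too strong to call the first-only rule an error.

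First-only does cost precision for three features. Using both acquisitions as clustered observations would lower the AUC standard error by about 19% at ICC 0.5, 9 to 13% at 0.7 to 0.8, and 3 to 5% at 0.9 to 0.95, with the estimand unchanged. This rests on assumed ICCs, on 3 malignant and 1 benign lesion per subject, and on a within-subject correlation of 0.5. For a feature with AUC near 0.70 the conclusion under the 0.5 rule hardly moves in this model. For weaker features, near 0.60, it can. The stated 18% precision and 80% power are unaffected.

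**What to change.** In Section 6.11.3.3, replace the first-only sentence with: *Both repeated measurements of T2\*, ADC and shear modulus enter the per-feature ROC analyses as separate observations of the same lesion, with the subject as the cluster.* State the same rule in the primary analysis plan in Section 9.2, and say that the repeats are not averaged.

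In the plan for secondary aim 1, specify one row per lesion using the first acquisition, and delete the reference to several observations per lesion, because the other 18 features are not repeated.

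The cost is wording, slightly more analysis work, and a row structure for three features that differs from the rest. No new data are needed. If the investigators prefer uniformity, the minimum is to keep first-only, restate it in Section 9.2, and remove the reference to repeats from secondary aim 1.
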